### **9.3.3 Post-vaccination Procedures (Day 1 and Day 29 [Cohort 1] and Day 1, Day 56, and Day 112 [Cohort 2])**

The following post-vaccination procedures will be performed on Day 1 and Day 29 (Cohort 1), and Day 1, Day 56, and Day 112 (Cohort 2).

- Careful training of the subject's LAR on how to measure local AEs and body temperature, how to complete the diary card, and how often to complete the diary card. Training should be directed at the individual(s) who will perform the measurements of local AEs and those who will enter the information into the diary card. This individual may or may not be the subject's LAR, but if a person other than the subject's LAR enters information into the diary card, this person's identity must be documented in the trial file and this person must receive training on the diary card. Training of the subject's LAR on how to measure an injection site reaction should be performed while the subject is under observation after vaccination.

Diary card instructions must include the following:

- The subject's LAR must understand that timely completion of the diary card on a daily basis is a critical component of trial participation. The subject's LAR should also be instructed to write clearly and to complete the diary card in pen. Any corrections to the diary card that are

performed by the person completing the diary card should include a single strikethrough line with a brief explanation for any change and be initialed and dated.

Please note:

Diary cards will be the only source document allowed for remote collection of solicited local and systemic AEs (including body temperature measurements). The following additional rules apply to the documentation of safety information collected by diary card:

- The Diary Card should be reviewed with the subject's LAR.
- No corrections or additions to the diary card will be allowed after it is reviewed with the investigator/designee.
- Any data that is identified as implausible or incorrect, and confirmed by the subject's LAR to be a transcription error should be corrected by the subject's LAR on the diary card (the correction should include a single strikethrough line and should be initialed and dated by the subject's LAR).
- Any blank or illegible fields on the diary card not otherwise corrected as above will be missing in the eCRF.
- The site must enter all readable entries on the diary card into the eCRF.
- Any newly described solicited safety information should be added to the diary card by the subject's LAR or by the person who is authorized by the subject's LAR to complete the diary, then initialed and dated. Any new unsolicited safety information such as a verbally reported event, should also be recorded in the subject medical chart (as recorded on the diary card/source document) and captured as an AE and recorded in the AE eCRF.
- Starting on the day of vaccination, the subject's LAR will check for specific types of events at the injection site (solicited local AEs), any specific generalized symptoms (solicited systemic AEs), body temperature (any method), any other symptoms or change in the subject's health status, and any medications taken (excluding vitamins and minerals). These solicited AEs and body temperature will be recorded in the diary. Assessments should preferably take place in the evening at day's end.
- Temperature measurement is to be performed using the thermometer provided by the site. If the subject feels unusually hot or cold during the day, the subject's LAR should check their temperature. If the subject has fever, the highest body temperature observed that day should be recorded on the diary card.
- The measurement of solicited local AEs (erythema, swelling, and induration) is to be performed using the ruler provided by the site.
- The collection on the diary card of body temperature, solicited local AEs, and solicited systemic AEs will continue for a total of 7 days following vaccine administration. The collection on the diary card of unsolicited AEs and medications will continue for 28 days following vaccine administration.

**CONFIDENTIAL**

After vaccination, the subject will be observed for at least 30 minutes, including observation for unsolicited AEs, solicited AEs, and body temperature measurement. The investigator or delegate will take the opportunity to remind the subject's LAR how to measure solicited reactions and body temperature as part of this observation period. All safety data will be collected in the subject's source documents.

The site should schedule the post-vaccination reminder calls (Days 3, and 32 for Cohort 1, and Days 3, 59, and 115 for Cohort 2).

The subject's LAR will receive a written reminder of the next planned trial activity. The subject's LAR will be reminded to complete the diary card daily, to contact the site if there are any questions, and to contact the site immediately (or as soon as the subject is medically stable) if the subject has a medical condition that leads to a hospitalization or an emergency room visit. All contact details will be provided to the subject's LAR by the responsible site staff.

#### **9.3.4        Clinic Visits after Vaccination**

Clinic visits that do NOT include a vaccination will be performed on Day 8, Day 36, Day 57, and Day 210 (Cohort 1) and Day 8, Day 29, Day 63, Day 84, Day 119, Day 140, and Day 293 (Cohort 2).

At each visit a brief symptom-directed physical assessment may be performed, including (but not limited to) the measurement of vital signs. Corresponding information will be documented in the source documents and eCRFs.

Blood should be taken from the subject using an aseptic venipuncture technique for serological immunogenicity testing as described in Sections [9.1.6](#) and [9.1.8](#). Refer to the detailed collection and handling procedures outlined in the Procedures Manual.

The site should schedule the next trial activity clinic visit with the subject's LAR.

The subject or the subject's LAR will receive a written reminder of the next planned trial activity. The subject or the subject's LAR will be reminded to contact the site if there are any questions and to contact the site immediately (or as soon as the subject is medically stable) if the subject has a medical condition that leads to a hospitalization or an emergency room visit.

#### **9.3.5        Phone Contacts – Safety Data Collection (Day 134 [Cohort 1] and Days 200 and 260 [Cohort 2])**

Safety calls will be performed on Day 134 for subjects in Cohort 1 and on Days 200 and 260 for subjects in Cohort 2. Safety calls are calls made to the subject by a trained healthcare provider. These calls will follow a script which will facilitate the collection of relevant safety information. The subject's LAR will be interviewed according to the script, and information relating to SAEs, and concomitant medications or vaccinations associated with those events must be written down. All safety information described by the subject must be written down in a designated location within the source documents and not written on the script used for the telephone call. The site should schedule the next safety call or clinic visit with the subject's LAR. The subject or the

subject's LAR will be reminded to contact the site if there are any questions and to contact the site immediately (or as soon as the subject is medically stable) if the subject has a medical condition that leads to a hospitalization or an emergency room visit.

#### **9.3.6 Phone Contacts - Reminder Calls (Day 3 and Day 32 [Cohort 1] and Day 3, Day 59, and Day 115 [Cohort 2])**

Post-vaccination reminder phone calls will be performed on Day 3 and Day 32 (Cohort 1) and on Day 3, Day 59, and Day 115 (Cohort 2). The purpose is to remind the subject or the subject's LAR about completion of the diary card. It is a conversation that follows the reminder telephone call script provided to the site (refer to the Procedures Manual), and it is not intended to be a call for collection of safety data. If the subject or the subject's LAR wishes to describe safety information, this information should only be collected by a trained healthcare professional at the site, and the safety data described must be written down in source documents. The subject or the subject's LAR should be reminded to write the information down in the diary card and to contact the site via the telephone number provided in the informed consent to discuss medical questions.

#### **9.3.7 Final Visit**

The final visit will be performed on Day 210 for Cohort 1, and Day 293 for Cohort 2. If a subject terminates earlier, standard visit procedures should be performed if possible (ie, Day 210 procedures for Cohort 1, and Day 293 for Cohort 2). For all subjects receiving an investigational vaccine, the investigator must complete the End-of-Trial eCRF page.

After trial exit and outside the context of this trial, a licensed benefit vaccine may be offered to all enrolled subjects. The choice of this vaccine will be discussed between the sponsor and the investigator, and will need to be approved by the appropriate ethics committee. This licensed benefit vaccine would only be administered according to the labelling approved in the country.

#### **9.3.8 Post-Trial Care**

No post-trial care will be provided.

### **9.4 Biological Sample Retention and Destruction**

In this trial, specimens for immune response testing will be collected as described in Sections 9.1.6 and 9.1.8. After blood draw and serum processing, the serum samples will be preserved and retained at a central laboratory that was contracted by the sponsor for this purpose for up to but not longer than 20 years or as required by applicable law. The sponsor has put into place a system to protect the subjects' personal information to ensure optimal confidentiality and defined standard processes for sample and data collection, storage, analysis, and destruction.

## **10.0 AEs**

### **10.1 Definitions**

#### **10.1.1 AEs**

An AE is defined as any untoward medical occurrence in a clinical investigation subject administered a vaccine. Adverse medical occurrences that occur after the ICF and assent form (where applicable) have been signed but before administration of the vaccine are documented in the Medical History. An AE does not necessarily have a causal relationship with investigational vaccine administration.

An AE can therefore be any unfavorable and unintended sign (eg, a clinically significant abnormal laboratory finding), symptom, or disease whether or not it is considered related to the investigational vaccine.

AEs will be graded by the investigator using the following categorical descriptors:

Mild (Grade 1)	Awareness of symptoms that are easily tolerated, cause minimal discomfort, and do not interfere with everyday activities.
Moderate (Grade 2)	Sufficient discomfort is present to cause interference with normal activity.
Severe (Grade 3)	Extreme distress, causing significant impairment of functioning or incapacitation. Prevents normal everyday activities.

Relatedness to vaccine will also be assessed by the investigator. SAEs will be reported to the sponsor within 24 hours of the investigator becoming aware of the event.

Please note: any solicited AE that meets any of the following criteria must also be entered as an AE on the Adverse Event eCRF.

- Solicited local or systemic AEs that lead the subject to withdraw from the trial.
- Solicited local or systemic AEs lasting beyond 7 days after vaccination (including day of vaccination).
- Solicited local and systemic AEs that lead to the subject being withdrawn from the trial by the investigator.
- Solicited local and systemic AEs that otherwise meet the definition of an SAE (see Section 10.1.5).

### **10.1.2 Causality of AEs**

Relatedness to vaccine will also be assessed by the investigator. The relationship of each AE to investigational vaccine(s) will be assessed using the following categories:

Related: An AE that follows a reasonable temporal sequence from administration of an investigational vaccine, and for which reasonable possible involvement of the investigational vaccine can be argued, although factors other than the investigational vaccine, such as underlying diseases, complications and concomitant drugs, may also be responsible.

Not Related: An AE that does not follow a reasonable temporal sequence from administration of an investigational vaccine and/or that can reasonably be explained by other factors, such as underlying diseases, complications, and concomitant drugs.

### **10.1.3 Relationship to Trial Procedures**

Relationship (causality) to trial procedures should be determined for all AEs.

The relationship should be assessed as “Yes” if the investigator considers that there is reasonable possibility that an event is due to a trial procedure. Otherwise, the relationship should be assessed as “No.”

### **10.1.4 Additional Points to Consider for AEs**

An untoward occurrence generally may:

- Indicate a new diagnosis or unexpected worsening of a pre-existing condition. Intermittent events for pre-existing conditions or underlying disease should not be considered as AEs.
- Necessitate therapeutic intervention.
- Require an invasive diagnostic procedure.
- Require investigational vaccine delay or discontinuation or a change in concomitant medication.
- Be considered unfavorable by the investigator for any reason.

Diagnoses versus signs and symptoms:

- Each event should be recorded to represent a single diagnosis. Accompanying signs (including abnormal laboratory values) or symptoms should NOT be recorded as additional AEs. If a diagnosis is unknown, sign(s) or symptom(s) should be recorded appropriately as an AE(s).

Worsening of AEs:

- If the subject experiences a worsening or complication of an AE after any administration of the investigational vaccine, the worsening or complication should be recorded as a new AE. Investigators should ensure that the AE term recorded captures the change in the condition (eg, “worsening of...”).

**CONFIDENTIAL**

Changes in severity of AEs:

- If the subject experiences changes in severity of an AE, the event should be captured once with the maximum severity recorded.

Preplanned surgeries or procedures:

- Preplanned procedures (surgeries or therapies) that were scheduled prior to signing of informed consent are not considered AEs (but will be recorded in the subject's medical history). Complications resulting from any planned surgery should be reported as AEs.

Elective surgeries or procedures:

- Elective procedures performed where there is no change in the subject's medical condition should not be recorded as AEs, but should be documented in the subject's source documents. Complications resulting from an elective surgery should be reported as AEs.

Follow Up:

- All AEs will be monitored until resolution or a stable status is reached or until a formal diagnosis can be made. AEs will not be monitored beyond Day 210(Cohort 1) or Day 293 (Cohort 2), unless deemed necessary by the sponsor.

### **10.1.5 SAEs**

An SAE is defined as any untoward medical occurrence that at any dose:

a. Results in DEATH.

Is LIFE THREATENING.

- The term "life threatening" refers to an event in which the subject was at risk of death at the time of the event; it does not refer to an event that hypothetically might have caused death if it were more severe.

Requires inpatient HOSPITALIZATION or prolongation of existing hospitalization.

Results in persistent or significant DISABILITY/INCAPACITY.

Is an IMPORTANT MEDICAL EVENT that satisfies any of the following:

- May require intervention to prevent items 1 through 4 above.
- May expose the subject to danger, even though the event is not immediately life threatening or fatal or does not result in hospitalization.

## **10.2 Procedures**

### **10.2.1 Collection and Reporting of AEs**

Please refer to Section [10.2.2](#) for Collection and Reporting of SAEs.

**CONFIDENTIAL**

#### 10.2.1.1 AE Reporting

All subjects experiencing AEs within 28 days of each study dose, whether considered causally related with the use of the investigational vaccine or not, must be monitored until symptoms subside and any abnormal laboratory values have returned to baseline, or until there is a satisfactory explanation for the changes observed, or until death, in which case a full pathologist's report should be supplied, if possible. All findings must be reported on an Adverse Event eCRF and on the SAE form, if applicable (see Section 10.2.2), which is part of the Investigator Site File. All findings in subjects experiencing AEs must also be reported in the subject's medical records. AE reporting beyond Day 57 (Cohort 1) or Day 140 (Cohort 2) will be spontaneous, at safety calls, or retrospectively at Day 210 (Cohort 1) or Day 293 (Cohort 2).

The following information will be documented for each event:

- Reported term for the AE.
- Start and end date.
- Serious (Y/N)?
- Severity.
- Investigator's opinion of the causality (relationship) between the event and administration of investigational vaccine(s) ("related" or "not related").
- Investigator's opinion of the causality (relationship) to trial procedure(s), including the details of the suspected procedure.
- Action taken with study treatment (investigational vaccine).
- Outcome of event.

#### 10.2.2 Collection and Reporting of SAEs

Collection of SAEs will commence from the time that the subject is administered the first study dose (Day 1). Routine collection of SAEs will continue until the end of the trial (All subjects experiencing AEs within 28 days of each study dose, whether considered causally related with the use of the investigational vaccine or not, must be monitored until symptoms subside and any abnormal laboratory values have returned to baseline, or until there is a satisfactory explanation for the changes observed, or until death, in which case a full pathologist's report should be supplied, if possible. All findings must be reported on an Adverse Event eCRF and on the SAE form, if applicable, which is part of the Investigator Site File. All findings in subjects experiencing AEs must also be reported in the subject's medical records. AE reporting beyond Day 57 (Cohort 1) or Day 140 (Cohort 2) will be spontaneous, at safety calls, or retrospectively at Day 210 (Cohort 1) and Day 293 (Cohort 2).

SAEs should be reported according to the following procedure:

A sponsor SAE form must be completed, in English, and signed by the investigator immediately or within 24 hours of first onset or notification of the event. The information should be completed as fully as possible but contain, at a minimum:

- A short description of the event and the reason why the event is categorized as serious.
- Subject identification number.
- Investigator's name.
- Name of the investigational vaccine(s) –in a blinded way in blinded trials.
- Causality assessment.

The SAE form should be transmitted within 24 hours to the attention of the contact(s) in the list provided to each site.

### **10.3 Follow-up of SAEs**

If information not available at the time of the first report becomes available at a later date, the investigator should complete a follow-up SAE form or provide other written documentation and fax it immediately within 24 hours of receipt. Copies of any relevant data from the hospital notes (eg, laboratory tests, discharge summary, and postmortem results) should be sent to the sponsor.

All SAEs should be followed up until resolution or permanent outcome of the event or is otherwise explained. The timelines and procedure for follow-up reports are the same as those for the initial report.

#### **10.3.1 Safety Reporting to Investigators, IRBs or IECs, and Regulatory Authorities**

The sponsor will be responsible for reporting all suspected unexpected serious adverse reactions (SUSARs) and any other applicable SAEs to regulatory authorities, including the European Medicines Agency (EMA), the Food and Drug Administration (FDA), investigators and IRBs or IECs, as applicable, in accordance with national regulations in the countries where the trial is conducted. Relative to the first awareness of the event by/or further provision to the sponsor or sponsor's designee, SUSARs will be submitted within 7 days for fatal and life-threatening events and 15 days for other SUSARs, unless otherwise required by national regulations. The sponsor will also prepare an expedited report for other safety issues where these might materially alter the current benefit-risk assessment of an investigational medicinal product or that would be sufficient to consider changes in the investigational vaccine administration or in the overall conduct of the trial. The investigational site also will forward a copy of all expedited reports to their IRB or IEC in accordance with national regulations.

#### **10.3.2 Post-Trial Events**

Any related SAEs that occur outside of the protocol-specified observation period or after the end of the trial must be reported to the sponsor. These AEs will be processed by the sponsor's

Pharmacovigilance Department. Instructions for how to submit these AEs will be provided in a handout in the Investigator Site File.

## 11.0 TRIAL-SPECIFIC REQUIREMENT(S)

### 11.1 Trial-Specific Committees

An independent DMC will be used for this trial as described in Section [11.1.1](#).

#### 11.1.1 Independent DMC

An independent program level DMC will assess safety data on an ongoing basis. The DMC will also have study level responsibilities to review data and make recommendations about the sequential enrollment of various groups and formulation arms in this study.

Enrollment in this study will be initiated sequentially based on age groups and formulation arms, with ongoing DMC review.

The DMC will be composed at a minimum of 2 members with pediatric infectious disease and/or vaccine expertise, and a clinician and statistician. The DMC will monitor safety during the study and can meet ad hoc, as necessary. The roles and responsibilities of the DMC will be described in the DMC charter.

In the event that safety monitoring uncovers an issue that needs to be addressed by unblinding at the group level, only members of the DMC can conduct additional analyses of the safety data.

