**Figure 6-a Schematic of Trial Design**

\* Recently manufactured clinical trial material lots

A total of 840 healthy subjects will be enrolled within two cohorts and randomized to vaccine regimen as follows:

- Cohort 1, N= 480, consisting of Group 1: aged 4 to less than 9 years; Group 2: aged 1 to less than 4 years; Group 2a: aged 1 to less than 4 years; Group 3: aged 6 months to less than 1 year (N= 120 each): subjects will be randomized with equal probabilities to 1 of the 8 unique combinations of formulation arms and dose groups (ie, 4 formulation arms and 1 or 2 doses). The additional 120 children, designated as Group 2a, are being included to evaluate the

recently manufactured NoV bivalent VLP vaccine formulations prior to enrolling children in Groups 3 and 4. Each of the combinations in Groups 1, 2, 2a, and 3 will consist of approximately 15 subjects per group. Thus Cohort 1 consists of 480 subjects in Groups 1, 2, 2a, and 3 combined.

- Cohort 2 (Group 4: aged 6 weeks to less than 6 months): 360 subjects will be randomized to receive the recently manufactured NoV bivalent VLP vaccine with equal probabilities to 1 of the 8 unique combinations of formulation arms and dose groups (ie, 4 formulation arms and 2 or 3 doses). Each of the combinations will consist of approximately 45 subjects.

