An independent program level Data Monitoring Committee (DMC) has been established to assess safety data on an ongoing basis. The DMC will also have study level responsibilities to review data and make recommendations about the sequential enrollment of various groups and formulation arms in this study (see Section 11.1.1).

Interim analyses will be performed after the primary safety and immunogenicity data are available

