#### **8.3 Randomization Code Creation and Storage**

Randomization personnel of the sponsor or designee will generate the randomization schedule. Randomization information will be stored in a secured area, accessible only by authorized personnel.

Randomization will be stratified by country and group: Group 1 (age 4 to less than 9 years); Groups 2 and 2a (age 1 to less than 4 years); Group 3 (age 6 months to less than 12 months); and Group 4 (age 6 weeks to less than 6 months). On Day 1, qualified subjects will be randomized using the IWRS to a formulation arm and number of doses depending on their age at the time of enrollment.

Randomization into groups and formulation arms will be restricted during various stages of the study as described previously in the protocol (section 6.1) based on DMC review of data from certain groups/arms prior to opening enrollment to other groups (see Section 11.1.1).

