### 7.8.1 Primary Immunogenicity Endpoint(s)

The primary immunogenicity endpoint for this trial is seroresponse rate, defined as the percentage of subjects with a 4-fold rise or greater, in serum anti-NoV antibody titers for both GI.1 VLP and GII.4 VLP as measured by Pan-Ig ELISA at Day 57 (Cohort 1) and Day 140 (Cohort 2). The primary analyses will be based on the PPS data but will also be provided using the FAS.

The seroresponse rates and 95% CIs will be summarized (as described in the General Methodology of Section 7.9) for each of the 8 formulation/dose combinations (4 formulation arms; 1 and 2 [or 2 and 3] doses), by group. These summaries will also be provided at the cohort level (pooling subjects across groups in Cohort 1). The 95% CI of seroresponse rate will be

calculated using the exact (Clopper-Pearson) method. These summaries will be provided for the subjects in the PPS and FAS.

Statistical analyses of the primary endpoint will be performed at the cohort level using the CMH method stratified by group to assess the effect of formulation/dose schedule. Common risk differences and corresponding 95% CIs will be provided for all pairwise comparisons of interest, without adjustments for multiplicity. The 14 comparisons of interest (listed in the *General Methodology* of Section 7.8 above) will be tested.

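### The documents contradict themselves on whether formulation arms open in stages or all 8 together within a group, and no planned analysis covers staged arms

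*Protocol*

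**What the plan says.** Arm-level staging appears in several places:

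- Protocol 11.1.1, repeated under Data Monitoring Committee in the Trial Summary (2.0): "Enrollment in this study will be initiated sequentially based on age groups and formulation arms, with ongoing DMC review".
- Protocol 8.3: "Randomization into groups and formulation arms will be restricted during various stages of the study". It refers back to section 6.1 for the detail.
- Protocol 6.1 and SAP 4.4: the DMC is to "make recommendations about the sequential enrollment of various groups and formulation arms in this study".

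The allocation text says something else. In Protocol 6.1, Cohort 1 "subjects will be randomized with equal probabilities to 1 of the 8 unique combinations of formulation arms and dose groups", and for Cohort 2 "360 subjects will be randomized to receive the recently manufactured NoV bivalent VLP vaccine with equal probabilities to 1 of the 8 unique combinations". SAP 4.4 says the same. The resulting sizes are given per group: "Each of the combinations in Groups 1, 2, 2a, and 3 will consist of approximately 15 subjects per group", and about 45 per combination in Cohort 2.

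A third description is by age alone. Protocol 13.1.1 and 13.1.3 and SAP 7.1 speak of an age step-down, and SAP 7.1 ties the opening of each successive age group to the DMC.

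On analysis, SAP 7.8.1 states: "Statistical analyses of the primary endpoint will be performed at the cohort level using the CMH method stratified by group". SAP 7.8 gives the ANCOVA terms as formulation/dose combination, log baseline, country, and for Cohort 1 also group, with a group-by-treatment interaction kept if its p-value is at most 0.05. Randomisation is stratified by country and group (Protocol 8.3). Neither document has an enrolment-stage term, a rule limiting comparisons to concurrent children, or a sensitivity analysis for staged arms.

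**The concern.** The primary objective is to select a formulation, so the between-formulation contrasts matter most. Randomisation protects them only if the arms compared were open to the same children at the same time. If one formulation opens later than another within a group, the contrast also carries whatever changed between the stages, such as natural norovirus exposure during follow-up or site mix. That is bias, and the planned confidence intervals do not reflect it.

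Stratifying by group does not help, because this confounding lies between arms inside a group. Cohort 2 is a single group, so its CMH analysis has no group stratum at all.

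The contradiction is also a practical problem. Whoever programs the IWRS cannot tell from the text whether to open 8 combinations at once or fewer. Section 8.3 sends the reader to 6.1, whose readable text gives no arm order, stage size or gating rule.

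**Working it through.** **1. The plan's own allocation figures.** Equal allocation over 8 combinations gives 120/8 = 15 per combination in each Cohort 1 group and 360/8 = 45 in Cohort 2. The total is 4 × 120 + 360 = 840. All three match Protocol 6.1.

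**2. Whether both rules can hold.** If only some combinations are open at a stage, a closed one has assignment probability 0 and the open ones more than 1/8. With two formulations open at two dose levels, for example, each of the 4 open combinations gets 1/4. Equal probability over 8 therefore fails at that stage, even if the final counts still reach 15 and 45.

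**3. Which comparisons are exposed.** SAP 7.8 lists 14 comparisons of interest. Four compare dose numbers within one formulation (A, B, C and D, once each). They are not exposed if both dose levels of a formulation open together. The other 14 − 4 = 10 are between formulations. The number that would be non-concurrent depends on the order, which the documents do not give:

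| Assumed order | Non-concurrent comparisons |
|---|---|
| A, then B, then C, then D | 10 |
| A and B, then C and D | 6 |
| A, then B, C and D | 4 |
| A, B and C, then D | 4 |

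**4. Effect on interval coverage.** The documents give no seroresponse rate and no drift, so these are assumptions: 60% seroresponse, no overlap in time between the two arms, and a shift b of 5, 10 or 15 points between stages.

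- SE = √(2 × 0.6 × 0.4 / n)
- Coverage = Φ(1.96 − b/SE) − Φ(−1.96 − b/SE)

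Cohort 2, 45 v 45: SE = √(0.48/45) = 0.103.

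| b | b/SE | Coverage |
|---|---|---|
| 0.05 | 0.484 | 0.930 − 0.007 = 92% |
| 0.10 | 0.968 | 0.839 − 0.002 = 84% |
| 0.15 | 1.452 | 0.694 − 0.000 = 69% |

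Pooled Cohort 1, 60 v 60 (4 groups × 15): SE = √(0.48/60) = 0.089. If only Group 3 were staged, and the four equal-sized groups carry equal weight, the pooled shift is b/4.

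| b in Group 3 | Pooled shift | Coverage |
|---|---|---|
| 0.05 | 0.0125 | 95% |
| 0.10 | 0.025 | 94% |
| 0.15 | 0.0375 | 93% |

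Coverage in pooled Cohort 1 would fall to 91%, 80% and 61% only if the same non-overlap and the same-direction shift occurred in all four groups.

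**The case against.** The strongest reply is that staging is by group and the arm-level words are loose or left over. Much supports this. The sentence in Protocol 8.3 ends by describing DMC review before other groups are opened. Protocol 13.1.1 and 13.1.3 and SAP 7.1 describe an age step-down. Protocol 4.2 has Group 2a wait until all four formulations are released, and Group 2a precedes Groups 3 and 4, so supply of the new lots gives no reason to stage arms later. Figure 6-a is not reproduced and the DMC charter is not available; either may settle the matter. A reader might infer that arms were staged and that the formulation contrasts are biased. The documents do not support that inference.

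A second reply is that the DMC may only advise which arms carry forward to the next group. Children within a group would then be randomised concurrently among the open arms, and the group stratum would suffice. This fits poorly with 11.1.1, where enrolment itself starts in sequence by arm, and with 6.1, which plans all 8 combinations in every group.

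A reader might also take the 80% coverage for pooled Cohort 1 as the expected size. It needs complete non-overlap in all four groups, including Groups 1 and 2, already fully enrolled (Protocol 4.2), and Group 2a, where the text points to concurrent arms.

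Some protection exists. Country is a randomisation stratum and an ANCOVA factor, though not a CMH stratum. Seroresponse is measured against the child's own baseline, which partly handles exposure before enrolment. The trial is descriptive (Protocol 13.3), so no power claim is at stake. That does not remove the issue, because 95% intervals and 14 tested comparisons are still planned to inform the choice of formulation.

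**Conclusion.** The point holds in conditional form. The current text contradicts itself: arm-level staging in Protocol 2.0, 6.1, 8.3 and 11.1.1 and SAP 4.4 cannot stand beside equal randomisation to all 8 combinations in each group. If the staging text were followed, up to 10 of the 14 listed comparisons would be non-concurrent, and nothing in the CMH or ANCOVA would correct for it.

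Cohort 2 carries most of the weight. It holds 360 of the 840 children, had not been enrolled at Protocol Version 4.0, and has no other group to dilute a shift. The coverage of 92%, 84% or 69% there rests on assumed drift, an assumed 60% seroresponse and complete non-overlap of two arms. It shows sensitivity and is not a forecast. Partial overlap would reduce the effect, and concurrent opening would remove it. For pooled Cohort 1, staging confined to Group 3 would cost one or two points of coverage at most under the same assumptions.

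**What to change.** **Protocol.** Reconcile 2.0, 6.1, 8.3 and 11.1.1, and with them SAP 4.4, for the groups still to be enrolled at Version 4.0 (2a, 3 and 4). State one of two things: all 8 combinations open together within each group, in which case the arm-level wording is deleted; or arms are staged, in which case the stages and the allocation at each stage are set out.

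**SAP 7.8.** Add that between-formulation comparisons use only concurrently randomised children. If any arm was opened, paused or closed separately within a group, make enrolment stage a CMH stratum and an ANCOVA factor, and a randomisation stratum for groups not yet enrolled.

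**Groups 1 and 2.** Wording cannot change their conduct. Tabulate enrolment dates by arm within each group to check concurrency.

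**Cost.** The work is protocol and SAP wording plus a stage variable from the IWRS. Where arms overlap only in part, some comparators are lost and intervals widen. Where two arms do not overlap at all, no concurrent comparators remain. That contrast cannot then be estimated concurrently and should be reported only as a descriptive, non-randomised comparison. If all arms open together, the analysis does not change.
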